Patient population	
 
Pragmatic approach to allow inclusion of wider cohort of patients than those with pure venous leg ulcers (VLU).
 
Therefore, patients with leg ulcer who are suitable for reduced (ie 'Lite') compression are considered for inclusion.
 
Specifically, these are: 
 
VLU
 
Mixed venous and arterial leg ulcers
 
 
 
Suitability for reduced compression is an ABPI of 0.5 -0.8 depending on holistic assessment. ABPI measured within last 3 months is part of the decision making to use reduced (Lite) rather than full compression. Only if ABPI or other diagnostic method (eg pulse palpation and ultrasound diagnostics, toe pressure assessment or arterial imaging) is not available or applicable then provision of solely a clinical assessment is allowed.
 

Sample size	
 
A total of 92 participants, over the age of eighteen, with leg ulcers. Power beta of 80%, one-sided alpha p-value of 0.025, non-inferiority limit 15%. Assumption of 15% difference in absolute percentage healed ulcers in intervention (Andoflex) arm versus control (Coban2) arm.
 
Therefore, 97.5% confidence interval for Andoflex to be no more than 15% worse than mean ulcers healed percentage for Coban2.
 
Sample size with 10% attrition rate included: 92 patients Of which: 
 
46 Patients to receive Andoflex TLC Calamine Lite
 
46 Patients to receive Coban2 Lite
 
 
 
Participants must have the capacity to provide informed written consent and complete patient reported outcome measures. Participants are recruited from the local community nursing caseload and identified in hospital clinics.
 

	Randomisation will be stratified for ulcer size, with cut-off	
	PUSH score of up to and including 10, or 11 and above.	
Sponsor	North Cumbria Integrated Care NHS Foundation Trust	
5001301	North Cumbra integrated care with roundation must	
Manufacturer & funder	Milliken Healthcare Inc	
	UK-based contact: [name], Clinical Specialist EMEA ,	
	Milliken Healthcare Division, [name] ,	
	[contact]	
Chief Investigator	[name], vascular specialist nurse, Vascular Surgery	
	Dept, North Cumbria University Hospitals NHS Trust.	
	[contact]	
Co-investigators	[name] PhD, Research Project Lead, [contact];	
	Cumbria Partnership NHS Foundation Trust	
	R&D Department, Carleton Clinic	
	[name]	
	[contact]	
	[name], GPwSI Research, Cumbria Partnership NHS	

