#### 6. SUBJECTS

#### 6.1 Anticipated number of research subjects

Locally, we have healing data available from two previous trials involving venous leg ulcers, namely the PREVUE and APRICOT trials (Jonker et al 2020a, and Jonker et al 2020b). One caveat is that those

studies concerned pure venous leg ulcers and that compression bandaging could be full (40 to 50mmHg) or Lite (20 to 30 mmHg). Nonetheless, from these studies we know that the study followup time points are valid and APRICOT compared Andoflex vs Coban2.

Below a summary is given for the sample size needed. The primary outcome, wound status (healed vs non-healed) is used for sample size calculation. The non-inferiority related sample size calculation has been performed using the calculator at https://www.sealedenvelope.com/power/binary-noninferior/. Power calculations for sample size assume 80% power and 2.5% one-sided confidence interval. The non-inferiority limit is set at 15% in favour of the Coban2 control bandage. The result is shown in Table 4. Since some patients may withdraw over the course of the 12-week trial period, a 10% dropout rate is calculated into the sample size. A 1:1 allocation to the two types of compression bandage will be applied.

	Sample size calculation	
	Intervention Bandage (Andoflex)	Control Bandage (Coban2)
Ulcer healed	65%	50%
Ulcer not healed	35%	50%
	Sample size required without any du Sample size with 10% attrition rate Total of 92 patients: - 46 Patients to receive Ando - 46 Patients to receive Coba	flex

Table 4, Sample size calculations

The CONSORT guidelines require a statement on the number of patients assessed for eligibility (Schulz, Altman & Moher 2010). The number of patients screened but who did not meet the inclusion criteria or who declined to participate will be recorded, as will any patients who are lot to follow-up (Appendix 5).

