## 8.2 Primary outcome statistics

The primary objective for this pilot study wound healed status at week 12. For non-inferiority analysis, patients who withdraw prior to completion of the study or do not attend week 12 appointment will be assigned the worst-case healing outcome (not healed at week 12).

The test for non-inferiority concerns the proportion of patients attaining ulcer closure by week 12 for both treatment groups, and the associated 97.5% one-sided confidence interval for the difference. Non-inferiority of Andoflex is considered valid if the lower limit of the 95% confidence interval for the difference between treatment means (Andoflex – Coban2) is not more negative than -15%. That is, non-inferiority for Andoflex is demonstrated when a maximum of 15% fewer patients using this bandage, compared with patients using Coban2, have healed by week 12 of treatment. This approach was taken in previous non-inferiority trials for ulcers (Harding et al, 2012; Moffatt et al, 2019), and is outlined in papers by Oczkowski (2014) and Flight (2016).

For comparative performance (superiority) analysis, any statistically significant difference (p-value < 0.05) between the two treatment arms will be determined with Chi-squared test. This will be done since Dunn et al postulate that non-inferiority and superiority trials effectively aim to answer the same hypothesis (Dunn et al, 2018)

Analysis will be performed on a per protocol and also an intention to treat basis. Multiple imputation (default five imputations) will be applied for missing values for the outcome measures, and inferential statistics will be performed on pooled data. Data will first be collated in Microsoft Excel, followed by analyses performed using SPSS v20.

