## 8.3 Secondary outcome statistics

To evaluate the effect of the different reduced compression bandages on leg ulcer healing, data from the two treatment arms will be compared.

Ulcer healing and more general health measures is assessed by the following parameters:

- Ulcer status (healed vs non-healed)
- Ulcer size (cm^2, measured with wound grid)
- PUSH score
- Visual analogue pain score
- Visual analogue pruritus score
- VEINES-QoL
- EQ-5D-5L

To assess the Ulcer size, PUSH score, visual analogue pain score, and visual analogue pruritus score, which are measured every 6 weeks, per treatment arm the average difference between time points will be calculated per treatment group (Wilcoxon test). To compare between the groups, Mann-Whitney U-test will be applied.

To measure patient-reported outcome measures on quality of life (VEINES-QoL and EQ-5D-5L) at baseline, week6 and week 12; the Wilcoxon test will be applied within treatment arms (over time) whereas the Mann-Whitney U-test will be performed between treatment arms. Data of the two treatment arms will be compared by applying the Mann-Whitney U-test.

Subject to sufficient data being available, Cox proportional hazards regression analysis will be conducted to investigate the role of the compression bandage itself and other covariates in leg ulcer healing rates. Other covariates include: leg ulcer size and chronicity at baseline, patient age, ulcer aetiology (pure venous vs other), absence/presence of co-morbidities, ulcer location, history of recurrent ulcers.

The following descriptive statistics will be reported on where possible:

- Number of patients screened
- Number of patients eligible/ineligible, and percentage of patients consented into the trial
- Number of patients completed the trial/discontinued (plus reasons if discontinued)

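### Section 8.2 pairs multiple imputation with chi-squared and rank tests that Rubin's rules cannot combine directly; testing a stacked file would give about 40% false positives instead of 5%

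*Protocol*

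**What the plan says.** Section 8.2 of the protocol states that "Multiple imputation (default five imputations) will be applied for missing values for the outcome measures" and that "inferential statistics will be performed on pooled data". It does not say whether pooling means combining five sets of results or testing one combined file.

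The analyses to which this could apply are:

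- **Non-inferiority (8.2):** a confidence interval for the difference in healed proportions at week 12. For this analysis the same section counts patients who withdraw or miss week 12 as not healed.
- **Superiority (8.2):** a chi-squared test at p < 0.05.
- **Secondary outcomes (8.3):** Wilcoxon tests within arms. Between arms, "the Mann-Whitney U-test will be performed between treatment arms". These cover ulcer size, PUSH, pain and pruritus scores, VEINES-QoL and EQ-5D-5L.
- **Cox regression (8.3):** only if the data suffice.

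The imputation sentence covers the outcome measures in general and does not exempt week-12 healing.

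**The concern.** Multiple imputation is valid when each completed dataset is analysed by itself and the estimates and their standard errors are then combined. The sentence in section 8.2, read word for word, reverses this order: the data are pooled and then tested. A file of five stacked copies counts every patient five times, so standard errors come out too small by a factor of √5, about 2.2.

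On the kinder reading, where pooling means Rubin's rules, a problem remains. Those rules need an estimate and a standard error from each dataset. Chi-squared, Wilcoxon and Mann-Whitney tests supply neither. For the secondary outcomes imputation is the only missing-data rule stated, and the only group comparison named is one that does not combine. The analyst has to improvise, and stacking is the most literal way to follow the text. The superiority claim and most of the secondary comparisons are at stake.

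**Working it through.** **Inputs.** The Research Protocol Summary and section 6.1 give a one-sided alpha of 0.025, 80% power, a 15-point margin, healing of 65% (Andoflex) and 50% (Coban2), and 46 patients per arm; "a 10% dropout rate is calculated into the sample size". Section 8.2 gives m = 5 imputations.

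**The plan's own figure.** n per arm = (0.65×0.35 + 0.50×0.50) × (1.960 + 0.842)² / (0.15 + 0.15)² = 0.4775 × 7.849 / 0.09 = 41.6, so 42 per arm and 84 in all. Unrounded, 2 × 41.6 / 0.9 = 92.5. The stated 92 is reproduced, so 46 per arm with 10% missing is a fair setting for the check.

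**Stacking, by formula.** With five copies the test statistic is √5 times too large. The one-sided error is 1 − Φ(1.96/√5) = 1 − Φ(0.877) = 19.0%, and the two-sided error is 38.1%. This ignores the added variation from imputing.

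**Stacking, by simulation.** There were 100,000 trials per scenario with 46 per arm. Week-12 status was missing at random with equal chance in both arms. Five imputations per arm were drawn from a beta posterior for the healing rate. The stacked analysis used 5 × 46 = 230 per arm. The Rubin analysis used total variance T = U + (1 + 1/5)B with t-based limits. Non-inferiority error was taken at a true difference of −15 points (35% v 50%, and 50% v 65%), and chi-squared error at 50% in both arms.

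| Missing | Non-inferiority, stacked (nominal 2.5%) | Non-inferiority, Rubin | Chi-squared, stacked (nominal 5%, two-sided) |
|---|---|---|---|
| 0% | 17.3-17.6% | 2.4% | 34.6% |
| 5% | 19.6-19.9% | 2.5-2.6% | 40.1% |
| 10% | 20.4-20.6% | 2.6-2.7% | 41.7% |
| 20% | 22.1-22.2% | 2.7% | 44.8% |

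A Mann-Whitney test on stacked normal data (4,000 trials) rejected in 39.1% of null trials with nothing missing and in 40.0% with 10% missing. The inflation comes mainly from the copying, so low dropout does not protect against it.

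**Which tests combine.** The difference in proportions has an estimate and a standard error, and the Rubin column shows that it keeps close to 2.5%. Cox coefficients combine in the same way. Chi-squared, Wilcoxon and Mann-Whitney do not.

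**Which rule governs week-12 healing.** If the worst-case rule applies, no week-12 status is left to impute in the non-inferiority test, and the second column of the table does not apply to it. The choice still matters: in the same simulations at 10% missing, the worst-case rule gave false non-inferiority in 3.4-3.5% of trials, against 2.6-2.7% with Rubin's rules.

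**Number of imputations.** At 10% missing the between-imputation variance B of the risk difference was 0.00118. The simulation noise is √(0.00118/5) = 1.5 points with five imputations and √(0.00118/50) = 0.5 points with 50. The sampling standard error is √(2 × 0.25/46) = 10.4 points.

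**The case against.** Pooled is the usual word for results combined across imputations, and no passage says that the datasets will be stacked. Combining rules are also often left to a statistical analysis plan, which may exist here. Both points stand as far as they go, and every stacking figure above is therefore conditional. They do not remove the mismatch. The protocol itself, in its own analysis section, fixes imputation together with chi-squared and rank tests, and on the kind reading these still lack a combining method. Rules for combining test statistics exist, but the protocol names none.

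Three stronger readings are tempting, and the documents do not support them:

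- **That the non-inferiority error is 20%.** Section 8.2 gives that analysis its own worst-case rule. The figure needs both stacking and imputation in place of that rule.
- **That none of the named tests can be combined.** The risk-difference interval and the Cox model can.
- **That five imputations are an error.** With Rubin's rules five hold 2.6-2.7%. The 1.5 points of noise are small beside a standard error of 10.4 points and are already counted in the (1 + 1/m)B term.

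Nor do the stacking figures carry over to averaged data, which keep 46 per arm. No error rate was calculated for that case.

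**Conclusion.** The point holds for the superiority test and the secondary tests. Whichever way the sentence is read, the plan gives no workable route from five imputed datasets to one chi-squared, Wilcoxon or Mann-Whitney result. If the datasets were stacked, the two-sided false-positive rate would be about 38-42% against a nominal 5%. The 38% comes from the formula and the 42% from the simulation at the protocol's 10% dropout; across 0-20% missing the simulated chi-squared rate runs from 35% to 45%. These figures assume values missing at random, equally in both arms.

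For the non-inferiority test the finding is narrower. Two missing-data rules overlap in section 8.2 and the text does not say which one governs. Only if imputation governs and the file is stacked would its error rise from 2.5% to about 20%. A reader should not infer that the trial's main conclusion is already compromised.

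**What to change.** 1. Replace the pooling sentence in section 8.2 with: *Each imputed dataset is analysed separately and estimates and standard errors are combined by Rubin's rules; no test is run on stacked or averaged data.*
2. State whether the worst-case rule or imputation (one of them) governs week-12 healing in the non-inferiority analysis.
3. Where imputation is used, analyse healing by a pooled risk difference, and PUSH, the two visual analogue scores, VEINES-QoL and EQ-5D-5L by a linear model adjusted for baseline value and PUSH stratum. Healed ulcers score zero on PUSH, so robust standard errors are sensible there.
4. Keep the rank tests, including the one for ulcer area, for observed data. Section 6.1 expects 50-65% of ulcers to heal, so area will pile up at zero and a model on a log scale would be hard to defend.
5. Optionally raise the number of imputations, for example to 50.

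The cost is a change of wording and a little computing time. Baseline values and the PUSH stratum are already collected, and no patients or visits are added.

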## 8.3 Secondary outcome statistics

To evaluate the effect of the different reduced compression bandages on leg ulcer healing, data from the two treatment arms will be compared.

Ulcer healing and more general health measures is assessed by the following parameters:

- Ulcer status (healed vs non-healed)
- Ulcer size (cm^2, measured with wound grid)
- PUSH score
- Visual analogue pain score
- Visual analogue pruritus score
- VEINES-QoL
- EQ-5D-5L

To assess the Ulcer size, PUSH score, visual analogue pain score, and visual analogue pruritus score, which are measured every 6 weeks, per treatment arm the average difference between time points will be calculated per treatment group (Wilcoxon test). To compare between the groups, Mann-Whitney U-test will be applied.

To measure patient-reported outcome measures on quality of life (VEINES-QoL and EQ-5D-5L) at baseline, week6 and week 12; the Wilcoxon test will be applied within treatment arms (over time) whereas the Mann-Whitney U-test will be performed between treatment arms. Data of the two treatment arms will be compared by applying the Mann-Whitney U-test.

Subject to sufficient data being available, Cox proportional hazards regression analysis will be conducted to investigate the role of the compression bandage itself and other covariates in leg ulcer healing rates. Other covariates include: leg ulcer size and chronicity at baseline, patient age, ulcer aetiology (pure venous vs other), absence/presence of co-morbidities, ulcer location, history of recurrent ulcers.

The following descriptive statistics will be reported on where possible:

- Number of patients screened
- Number of patients eligible/ineligible, and percentage of patients consented into the trial
- Number of patients completed the trial/discontinued (plus reasons if discontinued)

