#### 4.2 Secondary objective

To determine the efficacy of two-layer Lite compression bandaging for the management of leg ulcers at 6 and 12 weeks post-baseline

- Wound status (healed vs non-healed at 6 weeks)
- Healing rate (ulcer size, PUSH score)
- Leg ulcer related quality of life score (VEINES-QoL)

- Leg ulcer related pain and pruritus levels
- Generic quality of Life (EQ-5D-5L)

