#### 5.4 Follow-up and Standard care

Patients are in the study for the planned 12 weeks, even if the index leg ulcer has healed prior to that time point. Apart from the specific research measurements and assessments, the patient will be followed up as they would in normal clinical practice. The vascular or community nurse will redress the leg ulcer as per routine care, and will conduct the measurement of the leg ulcer (grid measurement and PUSH score). The researcher will visit the patient at baseline, week 6 and 12 of study participation to randomise the patient and conduct the questionnaires.

Patients identified in the community (primary care or non-vascular surgery dept) can be invited to participate in the study via the vascular surgery department.

Standard wound care will be provided throughout the trial period, as well as meeting any other medical needs that arise. The SIGN guidelines for leg ulcer care form the framework for management of the leg ulcers (https://www.sign.ac.uk/media/1058/sign120.pdf).

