#### 6.2.2 Exclusion criteria

- Under the age of 18 years
- Unable to fully understand the consent process and provide informed consent due to either language barriers or mental capacity
- Limited life expectancy, i.e. undergoing palliative care, or other condition that in opinion of researcher contraindicates participation

- Active infection in leg ulcer treated with antibiotics within last 1 week (does not apply for prophylactic antibiotic regimes)
- Is not willing or able to wear any compression device
- Pure foot ulcer, ie any ulcer that commences below malleolar region (particularly plantar, digital regions)
- Enrolled in other interventional research study related to patient's leg ulcer
- Previous participation in PEACH trial
- Awaiting surgical intervention related to vascular system of the lower limbs, planned within three months
- Wound size that is too small (typically < 1 cm^2), or too large (larger than single wound grid or extending round the leg) to measure accurately
- Known intolerance or allergy to materials used in compression bandaging (including zinc oxide, calamine).

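### Ulcer-size healing is scored as a cm² difference between visits, so if the between-arm test ranks these differences, a small ulcer that closes ranks below a large one that barely shrinks

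*Protocol*

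**What the plan says.** Protocol section 4.2 lists "Healing rate (ulcer size, PUSH score") among the secondary objectives, to be judged at 6 and 12 weeks after baseline. Section 8.3 fixes the scale as "Ulcer size (cm 2 , measured with wound grid"). For ulcer size, PUSH score and the two visual analogue scores, "which are measured every 6 weeks", it says that "per treatment arm the average difference between time points will be calculated per treatment group (Wilcoxon test"). The next sentence reads "To compare between the groups, Mann-Whitney U-test will be applied".

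The protocol nowhere gives a percentage, logarithmic or baseline-adjusted change in area. It does not list which pairs of visits are differenced, and it does not say how to score an ulcer already closed at the start of an interval.

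Two other sections bear on the point. Section 6.2.2 bounds ulcer size at entry: the lower bound is about 1 cm², and for the upper bound the criterion ends "or too large (larger than single wound grid or extending round the leg) to measure accurately". Section 5.4 keeps healed patients under observation: "Patients are in the study for the planned 12 weeks, even if the index leg ulcer has healed prior to that time point".

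**The concern.** A reduction in cm² can never exceed the area the ulcer started with. Across an entry range from about 1 cm² to a whole wound grid, the score therefore reflects starting size as much as healing. Complete closure, which is the trial's own definition of success in section 5.5.1, can receive a lower score than slight shrinkage of a large ulcer.

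A related problem arises if the week 6 to week 12 interval is analysed. An ulcer closed at week 6 has nothing left to lose, so an arm that closes more ulcers early contributes more zeros.

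At stake is the ulcer-size part of the healing-rate objective. It could point away from the primary result for arithmetic reasons alone, or miss a difference that a relative measure would detect.

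**Working it through.** The protocol states no figure on this point that could be reproduced, so the check applies its rule.

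**Inputs.** Size in cm² and differencing between visits (8.3). Visits at weeks 0, 6 and 12 (Table 3). Smallest eligible ulcer about 1 cm² (6.2.2). Largest eligible ulcer one wound grid, whose area is not given; 12 to 60 cm² is assumed below. The top PUSH size class is above 24.0 cm² (Appendix 1), so large ulcers are foreseen. Healing of 65% versus 50% and 46 patients per arm (Table 4).

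**1. Two records.** Score = size at the earlier visit − size at the later visit.
- Closed: 2 − 0 = 2 cm². As a percentage, 2/2 = 100%.
- Still open: 40 − 35 = 5 cm². As a percentage, 5/40 = 12.5%.

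The cm² score puts the open ulcer ahead by 5/2 = 2.5 times. The percentage puts the closed ulcer first.

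**2. How easily the order reverses.** A large ulcer of area L matches a closed ulcer of area s once it has shrunk by s/L.

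| Closed ulcer s | L = 12 cm² | L = 24 cm² | L = 40 cm² | L = 60 cm² |
|---|---|---|---|---|
| 1 cm² | 8.3% | 4.2% | 2.5% | 1.7% |
| 2 cm² | 16.7% | 8.3% | 5.0% | 3.3% |
| 4 cm² | 33.3% | 16.7% | 10.0% | 6.7% |

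**3. Weeks 6 to 12.** An ulcer of 6 cm² that is closed at week 6 and still closed at week 12 scores 0 − 0 = 0 for that interval, the same as an open ulcer that has not changed. From baseline to week 12 it scores 6 − 0 = 6. The problem is therefore confined to the later interval. The standard Wilcoxon signed-rank test also drops zero differences, so these patients leave the within-arm test.

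**4. Illustrative size.** The protocol gives no size distribution, so each model below is an assumption.
- Model A: baseline area a lognormal, median 5 cm², log SD 1.1, limited to 1–100 cm². Area at time t is a × max(0, 1 − t/T). T is lognormal with log SD 1.0, and its median is set so that 65% versus 50% close by week 12 (38% versus 25% by week 6). 46 per arm, Mann-Whitney test at p < 0.05.
- Model B: as A, but larger ulcers heal less often.
- Model C: 42 per arm, median 5 cm², log SD 1, limited to 1–80 cm². Half heal; the rest change by a uniform amount from 20% growth to 90% reduction. No difference between arms.

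| | A | B | C |
|---|---|---|---|
| Closed/unclosed pairs with the closed ulcer scored lower | 31% | 33% | 21% |
| Power, cm² change, weeks 0–12 | about 10% | 17% | – |
| Power, percentage reduction, weeks 0–12 | about 35% | 32% | – |
| Power, ranking week-12 cm² sizes | about 31% | – | – |

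In model A the mean week 6 to 12 change is 1.65 cm² in the better arm and 1.91 cm² in the worse arm, and the worse arm looks better on that interval in about 65% of trials.

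**The case against.** The strongest objection is that the quoted sentence is the within-arm step. The between-arm sentence does not say what is ranked. If sizes at each visit are ranked, every closed ulcer has size 0 and takes the best rank. The reversal then does not arise, and power in model A is about 31%, close to the 35% for percentage reduction. This stands. A reader might infer that section 8.3 settles on ranking differences, and that no other analysis could avoid the reversal; the text does not support either. Differences remain the plain reading, because they are the only derived quantity the paragraph names and the objective is a rate.

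The week 6 to 12 pair is also only inferred from the six-weekly schedule. Section 4.2 speaks of 6 and 12 weeks after baseline, which fits differences from baseline at least as well. A reader might infer that ulcers closed early will be scored as not healing; that follows only if this interval is used. The 65% figure carries the same condition.

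Other parts of the plan soften the effect. PUSH bands area: 40 to 35 cm² stays at sub-score 10, while 2 to 0 cm² falls from 4 to 0. Healed status is analysed at weeks 6 and 12, a Cox model with baseline size is planned if data suffice, and randomisation is stratified by PUSH at 10/11. All this limits the harm, but none of it changes how the cm² analysis scores a patient.

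A statistical analysis plan might settle the metric and the intervals. However, the protocol already states the scale and the differencing, so the point is fixed here and not merely left open.

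**Conclusion.** The point holds in a conditional form. Section 8.3 assesses ulcer-size healing by cm² differences and leaves open what the Mann-Whitney test ranks. If it ranks differences, closure of a small ulcer can rank below slight shrinkage of a large one. If a week 6 to 12 difference is used as well, an ulcer closed by week 6 and still closed counts as no healing.

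The reversal itself is arithmetic and needs no assumption beyond the eligible size range. Its frequency (21–33% of closed/unclosed pairs) and the power contrast (about 10–17% against 32–35%) rest on assumed sizes and healing patterns. The power figures also assume a true 65% versus 50% benefit, which is the planning assumption of a trial whose primary test is for non-inferiority. They show direction and rough size only.

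A reader might infer that the trial's healing conclusion is at risk. It is not: the primary endpoint and healed status at week 6 do not use this derivation. This is a cheap improvement to one component of a secondary objective.

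**What to change.** In section 8.3:
- Define ulcer-size healing as percentage area reduction from baseline, 100 × (baseline area − area at visit) / baseline area, at week 6 and at week 12. Set an ulcer that is closed at the visit to 100%, so that closure always takes the best rank.
- State that the Mann-Whitney test compares these percentages between the arms.
- State that the week 6 to week 12 difference is not used as a healing measure for ulcer size or for PUSH. Report baseline to week 6 and baseline to week 12 for both.
- Keep the cm² values as description.

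The cost is a few sentences, with no new data or visits. The downside is that percentage reduction is noisier for the smallest ulcers, where a small grid-reading error is a large share of the area. The rank test already planned limits that.

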#### 5.3 Recruitment

Participants will be randomised to one of two treatment arms. Patients in both groups will be given standard advice on leg ulcers and their management. Stratification by wound size (PUSH score up to and including 10 or PUSH score of 11 or higher) will take place.

All participants will have demographic data obtained and the following measures (table 3):

Weeks	0	2	4	6#	8	10	12#
Baseline measures (demographics,	Х						
medical history, vascular history)							
Ulcer wound status + bandage	Х			Х			Х
use status							
Ulcer size measured with wound	Х			Х			Х
grid							
PUSH score	Х			Х			Х
Visual analogue pain score	Х			Х			Х
Visual analogue pruritus score	Х			Х			Х
EQ-5D-5L	Х			Х			Х
VEINES-QoL	Х			Х			Х
Photo of ulcer (or original index	Х			Х			Х
site); subject to consent by patient							

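### Six secondary outcomes are compared between arms without adjustment for baseline or PUSH stratum, and the scale compared is not stated; the tests are valid but lose precision

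*Protocol*

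**What the plan says.** Section 8.3 of the protocol deals with the non-binary secondary outcomes in two groups.

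- **Ulcer size, PUSH, pain and pruritus.** Within arms, "per treatment arm the average difference between time points will be calculated per treatment group (Wilcoxon test"). For the arm comparison, "To compare between the groups, Mann-Whitney U-test will be applied". The text does not say whether that test is run on the differences or on the week 6 and week 12 values.
- **VEINES-QoL and EQ-5D-5L.** Here "the Wilcoxon test will be applied within treatment arms (over time) whereas the Mann-Whitney U-test will be performed between treatment arms". Again no scale is named for the arm comparison.

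Table 3 in section 5.3 schedules all six outcomes at weeks 0, 6 and 12. The same section says "Stratification by wound size (PUSH score up to and including 10 or PUSH score of 11 or higher) will take place", and section 6.1.1 repeats this.

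The only covariate-adjusted analysis is a conditional one: "Subject to sufficient data being available, Cox proportional hazards regression analysis will be conducted". It includes baseline ulcer size, but its outcome is healing, not any of these six measures. Section 8.2 adds multiple imputation for missing outcome values, after which "inferential statistics will be performed on pooled data".

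**The concern.** The trial collects a baseline value for every one of these outcomes and stratifies on one of them, but the arm comparisons adjust for neither. When an outcome is correlated with its own baseline, adjustment removes variation that has nothing to do with the bandage. Leaving it out makes the comparison noisier. With 46 patients per arm, it also leaves any chance baseline difference in the estimate. Section 8.1 will test for baseline differences, but section 8.3 gives these six comparisons no means of allowing for any that appear.

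The outcomes affected matter to the trial's rationale. The introduction cites an earlier comparison in which patients found Andoflex less itchy than Coban 2. Section 7.1 says the trial aims to establish whether some bandages control symptoms better. The pruritus, pain and quality-of-life comparisons bear on that directly.

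The unnamed scale is a second gap. Change scores and visit values can give different answers from the same data, so the choice should be fixed in advance.

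**Working it through.** **1. The plan's own figure.** The protocol gives no power figure for these secondary tests; its only one is the primary sample size. Inputs from section 6.1 (Table 4): 50% healed on control, 65% on Andoflex, margin 15%, one-sided 2.5%, power 80%.

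n per arm = (1.960 + 0.842)² × (0.50×0.50 + 0.65×0.35) / (0.15 + 0.15)² = 7.85 × 0.4775 / 0.09 = 41.6, so 42 per arm and 84 in total.

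Allowing for 10% dropout gives 84 × 1.1 = 93 or 84 / 0.9 = 94, close to the stated 92. This point does not change that number.

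**2. Variance of the arm difference.** Assume equal SD at baseline and follow-up (set to 1) and correlation r between them. The protocol gives no r, so a range is shown. In units of 2/n:

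- final value: 1
- change from baseline: 2(1 − r)
- baseline-adjusted (ANCOVA): 1 − r²

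| r | Final | Change | Adjusted | Reduction v final | Reduction v change |
|---|---|---|---|---|---|
| 0.3 | 1 | 1.40 | 0.91 | 9% | 1 − 0.91/1.40 = 35% |
| 0.5 | 1 | 1.00 | 0.75 | 25% | 1 − 0.75/1.00 = 25% |
| 0.7 | 1 | 0.60 | 0.51 | 49% | 1 − 0.51/0.60 = 15% |

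The adjusted analysis has the smallest variance in every row, so there is a gain whichever scale is meant.

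**3. What this means for the planned test.** The ratios above are for mean-based estimators. To bring in Mann-Whitney, take its efficiency under normality as 3/π = 0.955. Further assumptions, not in the protocol: 41 analysed per arm (46 × 0.9 = 41.4), two-sided 5%, and a true difference of 0.5 SD.

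Power = Φ(0.5 / (s × √(2/41)) − 1.96), where s is the square root of the variance in step 2 and 0.5 is multiplied by √0.955 for Mann-Whitney. For example, the adjusted analysis at r = 0.5 gives 0.5 / (0.866 × 0.2209) − 1.96 = 0.65, so power is 74%.

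| Analysis | r = 0.3 | r = 0.5 | r = 0.7 |
|---|---|---|---|
| Adjusted | 66% | 74% | 89% |
| Mann-Whitney, final value | 60% | 60% | 60% |
| Mann-Whitney, change | 46% | 60% | 81% |

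A simulation of 3,000 trials per r agreed: 64/73/87%, 59/58/59% and 46/59/81% respectively.

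The smallest difference detectable with 80% power is 0.63 SD for Mann-Whitney on final values, 0.75/0.63/0.49 SD on change, and 0.59/0.54/0.44 SD for the adjusted analysis.

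**4. Limits of the calculation.** Table 4 expects 50% to 65% of ulcers to heal, so about half or more of week 12 areas would be zero and PUSH scores would cluster at zero. The normal-theory figures do not carry over directly to those two outcomes. The calculation covers baseline adjustment only and gives no credit for the stratum term.

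**The case against.** The strongest reply is that Mann-Whitney is a defensible choice. It is valid under randomisation, suits skewed scores with many zeros, and is used only for secondary outcomes. Stratified blocks also limit imbalance in PUSH and, through it, in ulcer size. All of that stands. It makes this a matter of precision, not of error.

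Four stronger readings are tempting, and the protocol does not support them.

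- **That baseline values are discarded.** For size, PUSH, pain and pruritus, the sentence just before the arm comparison calculates differences between time points, so change scores may be meant. Baseline would then be used, though inefficiently.
- **That the quality-of-life scores are compared on raw visit values.** This is plausible, because no change score is mentioned for the arm comparison, but it is an inference. What can be shown is that no scale is named.
- **That a Mann-Whitney result cannot be pooled over imputations.** The associated probability that one arm exceeds the other has a standard error and can be combined, directly or on the logit scale; a Hodges-Lehmann shift with an interval is also available. The fair remark is that the protocol does not say how pooling would be done for these tests. The imputation sentence also stands under the primary outcome, although it speaks of outcome measures in the plural.
- **That the comparisons are biased.** Chance imbalance is already covered by the test's type I error.

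Nor are the within-arm Wilcoxon tests a mistake in themselves: the protocol does not use them to compare bandages.

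It could also be said that a statistical analysis plan may settle the scale. That answers only part of the point, because the protocol itself fixes the unadjusted test.

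**Conclusion.** The point holds as a loss of precision together with an unstated outcome scale. Six between-arm comparisons are fixed as unadjusted tests although the baseline values and the stratum will be on file. Under a normal linear model with r of 0.3, 0.5 or 0.7, adjustment cuts variance by 9%, 25% or 49% against final values and by 35%, 25% or 15% against change scores. The direction does not depend on which scale is meant. The size rests on the assumed correlations and on normality, and may differ for ulcer area and PUSH. The primary non-inferiority analysis and the target of 92 are not touched. This is a worthwhile improvement at almost no cost, not a threat to the trial's validity.

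**What to change.** Reword section 8.3 so that each of the six outcomes is compared between arms at weeks 6 and 12 by ANCOVA, or by one repeated-measures model covering both visits, with arm, the outcome's baseline value and PUSH stratum (up to 10, 11 or more) as terms. Report the adjusted difference with its 95% confidence interval. That estimate and its standard error also combine directly across the imputations described in section 8.2.

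For ulcer area and PUSH, specify a rank-based or ordinal baseline-adjusted version because of skew and zeros. Keep Mann-Whitney as a sensitivity analysis and state the scale on which it is run.

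The cost is a change of wording and a check of model assumptions. No additional data, visits or patients are needed.
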